## 10.2 Safety and Tolerability

### 10.2.1 Adverse Events

All adverse events will be coded using the Medical Dictionary for Regulatory Activities (MedDRA) and will be presented by Preferred Term within each MedDRA System Organ Class (SOC).

An adverse event will be defined as Treatment Emergent (TEAE) if the onset date is after the first intake of study medication.

Where dates are incomplete such that a decision cannot be made, it will be assumed that the adverse event is TEAE.

The incidence of the following events will be summarised by treatment group:

13. TEAEs by SOC and preferred term.
14. TEAEs by maximum severity.
15. TEAEs by strongest relationship to IP
16. Related TEAEs.
17. Potentially IMP-related (Related and Possibly Related) TEAEs.
18. Potentially IMP- TEAEs by maximum severity.
19. TEAEs with a fatal outcome.
20. Serious TEAEs.
21. Discontinuations due to TEAEs.

The frequency of TEAEs, by severity and IMP relationship, will be presented by treatment. The sampled and recorded observations of AEs will be considered to be discrete random variables. AEs will be analysed based on absolute risk or crude incidence rates or exposure-adjusted incidence rates using frequency statistics. The AE variable will be modelled as a Bernoulli distribution with parameter (p) representing the probability of success/occurrence. The definition of absolute risk applied in this analysis will be the following:

- The number of individuals experiencing an AE divided by the total number of participants in that dose treatment group.

Applicable only in the AE summary table14.3.1.8, the following definition of absolute risk will be used for this table:

- The number of AEs divided by the total number of AEs in that dose treatment group

Furthermore, these rates do not adequately account for an individual participant's profile of adverse events over the study period when a participant may remain in the trial after experiencing one or more events (i.e., occurrence of multiple events of the same kind or different kinds). Moreover, the required statistical assumptions (e.g., constant hazard rate over time) for valid estimates of incidence rates are not likely to be met in practice by adverse events data of clinical trials. To overcome this, mean cumulative function (MCF) will also be performed for the safety data. MCF is a nonparametric approach that provides a valid statistical inference on recurrent adverse event profiles of drugs in randomized clinical trials (RCT). The

RESP30X-EBA: Statistical Analysis Plan22 JUL 2024

estimate involves no assumptions about the form of MCF. As compared to the crude or exposure-adjusted incidence rates of adverse events, the MCF estimates facilitate more understanding of the safety profiles of a drug in an RCT. Survival analysis models to understand the probability of occurrence over time will be applied using the Kaplan-Meier, Cox-Proportion Hazard, and Binary Logistical Regression models. A special focus will be placed on Adverse Events that are considered related to study treatment.

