| Preferred term 2                          |                      |                  |                      |                  |                      |                  |                      |
| SOC2                                      |                      |                  |                      |                  |                      |                  |                      |
| Preferred term 3                          |                      |                  |                      |                  |                      |                  |                      |
| Preferred term 4                          |                      |                  |                      |                  |                      |                  |                      |
| <repeat for all SOC and Preferred Terms > |                      |                  |                      |                  |                      |                  |                      |
| <repeat for other groups>                 |                      |                  |                      |                  |                      |                  |                      |

RESP30X-EBA: Statistical Analysis Plan22 JUL 2024

Table 14.3.1.8: Summary of Frequency of Treatment Emergent Adverse Events  
Safety Population

| All participants
n (%)                  | RESP301tds
n (%) | RESP301qd
n (%) | RESP301bd
n (%) | RESP301tdsHRZ
n (%) |
|--|---------------------|--------------------|--------------------|------------------------|
| Number of TEAEs                            |                     |                    |                    |                        |
| Number of Serious TEAEs                    |                     |                    |                    |                        |
| Number of Grade 1 (Mild) TEAEs             |                     |                    |                    |                        |
| Number of Grade 2 (Moderate) TEAEs         |                     |                    |                    |                        |
| Number of Grade 3 (Severe) TEAEs           |                     |                    |                    |                        |
| Number of Grade 4 (Life-threatening) TEAEs |                     |                    |                    |                        |
| Number of Unrelated TEAEs                  |                     |                    |                    |                        |

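### For Table 14.3.1.8 the SAP calls a share of events an absolute risk, so an arm with more adverse events overall can show a lower percentage of serious, severe or related events

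*SAP*

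**What the plan says.** SAP 10.2.1 defines absolute risk twice. The general definition is participant-based: "The number of individuals experiencing an AE divided by the total number of participants in that dose treatment group". It follows a statement about the model: "The AE variable will be modelled as a Bernoulli distribution with parameter (p) representing the probability of success/occurrence". An exception comes next: "Applicable only in the AE summary table14.3.1.8, the following definition of absolute risk will be used for this table". For that table the measure is "The number of AEs divided by the total number of AEs in that dose treatment group".

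The shell in SAP 12.1 is titled "Table 14.3.1.8: Summary of Frequency of Treatment Emergent Adverse Events". Its columns are arms with a count and a percentage, and its rows count events: all TEAEs, then among others "Number of Serious TEAEs" and "Number of Grade 3 (Severe) TEAEs", with further rows for the other grades and for relatedness. Read together, the percentage in each row is the events in that category over all events in the same arm.

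**The concern.** A risk needs people, or people and time, in its denominator. Here the denominator is the total number of adverse events in the arm, which rises with the toxicity that the table is meant to describe. Each extra mild event lowers the percentage for the serious, severe and related rows even though nothing about those events has changed. The measure also does not fit the model stated in the same section, where p is a probability of occurrence.

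The total number of events may well differ between arms in this trial. The RESP301 arms range from one to three nebulisations a day, and protocol 2.2.3.1 names cough as the most frequent AE in the COPD/bronchiectasis group of an earlier RESP301 study. If mild cough rises with dosing frequency, which is an assumption, the most intensively dosed arm gets the largest denominator. Table 14.3.1.8 is also the compact display that sets grades 1 to 4 side by side across arms, so a reader would naturally compare its percentages.

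**Working it through.** The plan states no AE counts or rates, so there is no figure to reproduce. The check is direct arithmetic on assumed counts.

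**Inputs**
- Arm size n: 15 per arm (SAP 4.3). In Stage 1, 15 on RESP301 tds and 5 on HRZE (SAP 4.1, Table 2).
- T, all AEs in the arm, and s, severe AEs in the arm: assumed. The same arithmetic applies to serious or related events.
- Each severe event is assumed to fall in a different participant, so participants with an event = s.

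**Formulas**
- Table 14.3.1.8 measure = s/T
- Events per participant = s/n, which under the last assumption equals the SAP's general absolute risk

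**Step 1: the all-TEAE row.** Here s = T, so the figure is T/T = 100% in every arm with any AE. It carries no information.

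**Step 2: severe events fixed, mild events added.** With s = 3 and n = 15, the measure is 3/10 = 30.0%, 3/20 = 15.0%, 3/40 = 7.5% and 3/60 = 5.0%. The participant-based risk stays at 3/15 = 20.0% throughout.

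**Step 3: two arms of 15, A with 10 AEs and B with 40.**

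| Severe events, A and B | s/T, A and B | s/15, A and B | What s/T does |
|---|---|---|---|
| 3 and 3 | 30.0% and 7.5% | 20.0% and 20.0% | shows a difference where there is none |
| 3 and 6 | 30.0% and 15.0% | 20.0% and 40.0% | reverses the ranking |
| 2 and 8 | 20.0% and 20.0% | 13.3% and 53.3% | hides a fourfold difference |
| 1 and 10 | 10.0% and 25.0% | 6.7% and 66.7% | keeps the ranking, shrinks a tenfold ratio to 2.5 |

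**Step 4: when the busier arm looks better.** B shows the lower figure when s_B/T_B < s_A/T_A, that is, when s_B/s_A < T_B/T_A. Here T_B/T_A = 40/10 = 4. The ratios s_B/s_A in the four rows are 1, 2, 4 and 10, so B is lower in the first two rows, equal in the third and higher in the fourth.

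**Step 5: unequal arms in Stage 1.** Suppose both arms have 10 AEs, 3 of them severe. Both cells read 3 (30.0%). Per participant the rates are 3/15 = 0.20 and 3/5 = 0.60. Neither the count nor the percentage shows the threefold difference.

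**The case against.** The case for leaving the text alone has four parts.

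- **The exception is declared and its scope is narrow.** SAP 10.2.1 says that it applies to one table. The term absolute risk appears in the methods text, not in the shell, which is headed "Summary of Frequency of Treatment Emergent Adverse Events" and labels its rows as numbers of events. The participant tables are titled incidence and count subjects. This stands: a reader might infer that the finished table will present these percentages under the name absolute risk beside the participant-based risks, and the shells do not support that.
- **The real risks are reported elsewhere.** Participant-level tables cover serious TEAEs (14.3.1.1, 14.3.1.5), maximum severity (14.3.1.7.1), relatedness (14.3.1.3.1, 14.3.1.3.2, 14.3.1.7.3), and severity with relatedness (14.3.1.7.4). SAP 10.2.1 also names exposure-adjusted rates and plans a mean cumulative function for recurrent events. This stands and limits the harm. It does not make the percentage in Table 14.3.1.8 meaningful as a risk. Table 14.3.1.1 has no severity rows, and Table 14.3.1.7.1 stacks the arms in blocks, so neither gives the same side-by-side view.
- **No decision depends on it.** The safety criteria in SAP Section 9 are percentages of participants and are summarised in Table 14.3.7. This stands.
- **The counts are printed beside the percentages.** With equal arms, a reader who sees 3 (30%) and 6 (15%) can tell which arm has more severe events. This stands for arms of equal size. It fails in Stage 1, where the arms are 15 and 5 and the interim safety analysis follows Section 10.2.

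**Conclusion.** The definition is wrong as written and should change, but the point is small. A share of all events is not an absolute risk. It sets the first row to 100%, and it can create, hide or reverse a difference between arms.

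A reader might infer that the arm with more events always looks safer. That does not follow: it shows a lower figure only if its serious, severe or related events rise less than in proportion to its total. If they rise in proportion the figures are equal, and if they rise faster its figure is higher. Nor do the documents support the inference that the trial's safety conclusions or the decision to proceed to Stage 2 would be distorted, since both can draw on participant-level results.

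The size of the effect rests on assumed event counts, because the documents give none. Equating events per participant with participant risk assumes one such event per affected participant. The constant 100% row and the fall in the percentage as mild events are added follow from the definition, whatever the counts, provided the category has at least one event.

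**What to change.** 1. In SAP 10.2.1, reserve absolute risk for the participant-based definition and remove the term from the sentence about Table 14.3.1.8.
2. In Table 14.3.1.8, give for each row the number of events and the events per participant, with the number of participants in each column heading. Events per 100 participant-days is an alternative, with follow-up counted from first dose to the follow-up visit or last contact, in line with the AE collection period. Either makes the 15 and 5 participants of Stage 1 comparable.
3. If the event-based percentage is kept, head it as the percent of all TEAEs in the arm and leave it blank in the all-TEAE row.

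Deleting the second definition without a replacement is not enough, because the general definition counts individuals and does not fit rows that count events.

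The cost is a sentence or two in SAP 10.2.1 and revised column headings in one shell. No new data are needed and no other analysis changes. It should be done before the SAP is finalised, and before any interim output of this table is read by arm.

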#### 10.2.2 Study Stopping and Amendment Criteria

The study stopping and amendment criteria will be summarised as described in Section 9 in the form of frequency statistics per treatment group and time point.

#### 10.2.3 Other Safety Variables

##### Laboratory parameters

Laboratory safety tests are performed throughout the study. The data will be listed with values outside the normal range flagged and with the grade according to Common Terminology Criteria for Adverse Events (CTCAE) mentioned. The recorded values and the change from baseline will be summarized by treatment and time of collection. The assessment (normal/abnormal-NCS/ abnormal-CS as well as the grade according to CTCAE) will be summarized for haematology, blood chemistry, and urinalysis by treatment and time of collection.

##### Physical examination

The physical examination is repeated at each visit. The results (normal/abnormal-NCS/ abnormal-CS as well as the grade according to CTCAE, if applicable) will be summarized by body system by treatment and time of collection.

##### Vital signs

Vital signs are recorded at each visit. The change from the baseline will be calculated. The data will be summarized by treatment and time of collection.

##### Concomitant medication

Concomitant medication is defined as any medication taken within 14 days prior to IMP administration or during the trial until visit 19 (day 28). Where dates are incomplete such that a decision cannot be made, it will be assumed that a medication is concomitant. The incidence will be summarised by generic name, class, and treatment.

##### Methemoglobin

The assessment of Methemoglobin using Spmet will be summarized by single SpMet measurement and Highest SpMet measurement per treatment and time of assessment using descriptive statistics.

##### Lung Function

The assessment of lung function using Spirometry will be summarized by Forced Vital Capacity, Forced Expiratory Volume in 1 Second and Modified Tiffeneau-Pinelli index per treatment and time of assessment using descriptive statistics.

## 10.3 Early Bactericidal Activity (EBA)

The below provides a summary of the general planned EBA analysis, however, more elaborate model definitions and methodology will be provided in the EBA statistical report as EBA modelling is subject to the EBA data.

Exploratory graphical analysis of CFU and TTP data versus time following drug treatment. Covariate distributions will be inspected for the identification of potential outliers and to inform the analysis.

Development of population EBA models for CFU and TTP

- a) Evaluation of structural and stochastic models to describe CFU and TTP versus time profiles
- b) Investigation and characterization of covariate relationships that influence initial bacterial load and bacterial killing.

### 10.3.1 Structural Model (Fixed Effects)

A separate EBA model will be developed for each of the two endpoints TTP and CFU. For each model, mono- and bi-linear (for CFU only) and mono- and bi-exponential models will be fitted to the data as defined below for TTP and CFU:

Functions for TTP and CFU should be explored, if needed, and indicated by the EBA data:

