1.2. Evaluations

	Objective	Outcome Variable/s	Statistical Analysis
Primary: Activity	
Stage 1 To determine the EBA of inhaled RESP301 6 mL tds dosed via NEB over 14 consecutive days.
 
Stage 2: To determine the EBA of inhaled RESP301 6 mL dosed via NEB administered qd, bd, or tds in combination with HRZE, over 14 days of treatment to optimise the dosing schedule.
	
Overnight sputum collection from which viable mycobacteria in the sample is quantified:
 
 as TTP using the Mycobacteria Growth Indicator Tube (MGIT) (Bactec™ MGIT™ 960) system. 
The samples from participants receiving HRZE alone serve to confirm that the laboratory assays result in the expected EBA for HRZE, thereby validating the method.
	
The EBA_{TTP} (0-14) in the MGIT (Bactec™ MGIT™ 960) system as determined by the predicted rate of change in the TTP in sputum over the period Days 0 to 14 will be analysed using linear, bi-linear, or non-linear functions using nonlinear mixed effects modelling of TTP over time.
 
Predicted estimates of rates of change including uncertainties for the potential differences in treatment effects between the study arms will be determined and graphically illustrated.

Secondary: Activity	
Stage 1 To determine the EBA of inhaled RESP301 6 mL tds dosed via NEB over 14 consecutive days.
 
Stage 2: To determine the EBA of inhaled RESP301 6 mL dosed via NEB administered qd, bd alone, or tds in combination with HRZE, over 14 days of treatment to optimise the dosing schedule.
	
Overnight sputum collection from which viable mycobacteria in the sample is quantified:
 
 as CFU on a solid media culture. 
The samples from participants receiving HRZE alone serve to confirm that the laboratory assays result in the expected EBA for HRZE, thereby validating the method.
	
The EBA_{CFU} (0-14) as determined by the predicted rate of change in log₁₀CFU per mL sputum over the period day 0 - 14 will be described using linear, bi-linear or non-linear functions using nonlinear mixed effects modelling as dictated by the data of log₁₀CFU over time and in relation to drug exposure.
 
Predicted estimates of rates of change including uncertainties for the potential differences in treatment effects between the study arms will be determined and graphically illustrated.

	Objective	Outcome Variable/s	Statistical Analysis

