Secondary: Safety and tolerability	To determine the safety and tolerability of inhaled RESP301 6 mL via NEB administered qd, bd, and tds alone, or tds in combination with HRZE, over 14 days of treatment.	Measurement of: 
 • Adverse Events • Concomitant Medication • Safety Laboratory (Haematology, Chemistry, Urinalysis) • Methaemoglobin • Physical Examinations • Vital Signs • Body Mass Index (BMI). 	Incidence of Treatment Emergent Adverse Events (TEAEs) will be presented by severity, drug relatedness, seriousness, leading to early withdrawal and leading to death. Clinical laboratory measurements and vital signs will be summarized using descriptive statistics as actual values and changes from baseline. Physical examinations and concomitant medications will be listed.
Exploratory	To explore the EBA variability due to potential M.tb sterilisation in sputum samples as a result of NO contamination in sputum samples.	Overnight sputum collection from which viable mycobacteria in the sample is quantified as TTP using the MGIT (BactecTM MGIT™ 960) system.	Comparison of EBA _{TTP} (0-14) versus EBA _{TTP} (0-15) and the predicted EBA _{TTP} (14-15) versus observed EBA _{TTP} (14-15) analysed using linear and non-linear functions using mixed effects modelling of TTP over time and analysis of variance.

1.3. Study Flow Chart for Stages 1 and 2

Period	Screening			Treatment															FU 20 ^A	EWD	
	Visit 1	2	3	4	5	6	7	8	9	10	11	12	13	14	15	16	17	18	19		
Day (-9 to -3)	-2	-1	1	2	3	4	5	6	7	8	9	10	11	12	13	14	15	16	28		
Written Informed Consent	X																				
Demography	X																				
Medical & Treatment History	X																				
Physical Examination ^{B, C}	X			X	X	X	X	X	X	X	X	X	X	X	X	X	X	X	X	X	
Vital Signs ^C	X	X	X	X	X	X	X	X	X	X	X	X	X	X	X	X	X	X	X	X	
Height	X																				
IMP Administration ^D , and Compliance Check				X	X	X	X	X	X	X	X	X	X	X	X	X	X	X	X		
Concomitant Medication ^E	X	X	X	X	X	X	X	X	X	X	X	X	X	X	X	X	X	X	X	X	
Adverse Events ^F				X	X	X	X	X	X	X	X	X	X	X	X	X	X	X	X	X	
Eligibility Assessment ^G		X																			
EBA unit inpatient	X ^H	X	X	X	X	X	X	X	X	X	X	X	X	X	X	X	X	X	X ^I		
Randomisation ^J		X																			
Chest X-ray		X																			
Spot or Overnight Sputum ^{K, L}	X																				
Overnight Sputum ^{K, M}		X	X	X	X	X	X	X	X	X	X	X	X	X	X	X	X	X			
Safety labs (Haematology, Chemistry, Urinalysis) ^C	X			X								X								X	X
Methaemoglobin (SpMet) ^N	X			X								X								X	

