#### Mono-Linear and Mono-Exponential Model For TTP

##### 1) Logarithmic function:

$$TTP = e^{\alpha_{\log}} \cdot \log_{10}(t) + A_{\log}$$

The model includes one intercept defined by A and one slope defined by  $\alpha$ .

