##### 2) Exponential decay upwards function:

$$TTP = A_{\exp} + B_{\exp} \cdot (1 - e^{\alpha_{\exp} \cdot t})$$

The model includes one intercept defined by A, one asymptote defined as B, and one slope defined by  $\alpha$ .

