### **10.3.8 Final model**

A final model should provide a good description of the observed data, not have any important trends in the relevant GOF diagnostics, have a successful termination of the covariance step and preferably have a condition number less than 1000. Should a model be accepted as final without these criteria being met, it will be discussed and justified in the report.

There will be one final model for each of the endpoints.

Based on the final EBA models for TTP and CFU, mean bactericidal activity per treatment arm will be expressed as the daily change in TTP and CFU from day 0 to day 14. If required, periods from 0 to 2 days, 0 to 7 days, 7-14 days, or any other period will be predicted or calculated as well as the 95% Bayesian credibility interval using only the patient data included in the study. Clinical trial simulations ( $n= 1000$ ) will be used to predict mean (95% prediction interval) bactericidal activity for different treatment arms and different characteristics depending on the covariates included in the final models.

Early bactericidal activity data definition table (DDT): A separate data specification table will be created for EBA. The dataset should be in excel csv format. A readme file describing the dataset column names should be created with an example for 1 participant.

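### The SAP prints no straight-line or bi-linear TTP equation although the protocol names both, and its logarithmic form has no value at Day 0 and cannot express a zero or falling rate

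*SAP*

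**What the plan says.** Protocol 1.2 states that the primary endpoint, the rate of change in TTP over Days 0 to 14, "will be analysed using linear, bi-linear, or non-linear functions using nonlinear mixed effects modelling of TTP over time". For the exploratory comparison of Days 0-14, 0-15 and 14-15 it again includes a linear form: "analysed using linear and non-linear functions using mixed effects modelling of TTP over time and analysis of variance".

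SAP 10.3.1 announces that "mono- and bi-linear (for CFU only) and mono- and bi-exponential models will be fitted to the data as defined below for TTP and CFU". The TTP block is headed "Mono-Linear and Mono-Exponential Model For TTP", but its two equations are:

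- logarithmic: TTP = e^alpha x log10(t) + A, described as "The model includes one intercept defined by A and one slope defined by" alpha;
- rising exponential: TTP = A + B x (1 - e^(alpha x t)), described as "The model includes one intercept defined by A, one asymptote defined as B, and one slope defined by" alpha.

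Straight-line and bi-linear equations follow for CFU only. No bi-exponential TTP equation is printed either. The section adds one general opening: "Functions for TTP and CFU should be explored, if needed, and indicated by the EBA data".

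Four other parts of the SAP bear on this:

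- Section 9 makes progress to Stage 2 depend on the TTP rate in the RESP301 tds arm differing from zero at the 5% level.
- Section 7.1 defines time as the nominal sampling day and takes baseline from Days -2 and -1.
- Section 10.3.8 asks for a successful covariance step and says that the final model should "preferably have a condition number less than 1000".
- Section 11.3 (Tables 14.4.16 to 14.4.19) lists model-predicted TTP activity by day and for Days 0-2, 0-7, 0-14, 0-15 and 14-15.

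**The concern.** The simplest functions that the protocol names for its primary endpoint have no TTP equation in the SAP, and the one block labelled linear is not linear in time. Two consequences follow from the printed algebra alone. The logarithmic form cannot be evaluated where the endpoint begins. It also has no parameter value for no effect, although the Stage 2 criterion compares the rate with zero.

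A third consequence depends on the data. If TTP under RESP301 alone rises roughly steadily, neither printed curve suits it. One moves the rise into the first days; the other becomes poorly determined. At stake are the sub-period and daily tables and the Day 14-15 comparison, which the protocol uses to look for nitric oxide carry-over in sputum. A Day 14-15 prediction that is too low can create an apparent discrepancy or hide a real one.

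**Working it through.** The plan gives no figure for this point to reproduce. The equations are those of SAP 10.3.1. Exact linearity of the true rise is my assumption, used as a test case.

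**1. Day 0 and sign.** log10(0) does not exist, nor does log10 of -1 or -2, and the SAP states no shift of origin. Changes over 0-2, 0-7, 0-14 and 0-15 are therefore undefined as printed. Since e^alpha > 0 for every alpha, the logarithmic slope cannot be negative and reaches zero only as alpha goes to minus infinity.

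**2. Logarithmic curve fitted to a straight line.** Take a true TTP rise of 1 h/day, sampled on Days 1 to 14 without noise, and regress t on x = log10(t).

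- Sxx = 1.4693, Sxy = 17.2135, Stt = 227.5.
- Slope b = 17.2135 / 1.4693 = 11.715.
- r2 = 17.2135^2 / (1.4693 x 227.5) = 0.886.

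The predicted rate from day a to day c is b x log10(c/a) / (c - a):

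| Days | Calculation | Predicted / true |
|---|---|---|
| 1-2 | 11.715 x 0.3010 / 1 | 3.53 |
| 1-7 | 11.715 x 0.8451 / 6 | 1.65 |
| 7-14 | 11.715 x 0.3010 / 7 | 0.50 |
| 14-15 | 11.715 x 0.02996 / 1 | 0.35 |
| 1-14 | 11.715 x 1.1461 / 13 | 1.03 |

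These ratios do not depend on the size of the rise. If the origin is repaired with log10(t+1) on Days 0-14, the ratios are 2.95 (0-2), 1.60 (0-7), 0.48 (7-14), 0.35 (14-15) and 1.04 (0-14).

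**3. Exponential curve near a straight line.** I write the rise as A + B(1 - e^(-k t)) with k > 0; the printed exponent carries no minus sign. As k goes to 0 the curve tends to A + (B x k) t, so only the product B x k is determined. I computed the condition number of the correlation matrix of (A, B, k) for one curve sampled on Days 0 to 14. It does not depend on the total rise.

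| k per day | Rate on Day 14 / Day 0 | Corr(B, k) | Condition number |
|---|---|---|---|
| 0.10 | e^-1.4 = 0.25 | -0.925 | 215 |
| 0.05 | e^-0.7 = 0.50 | -0.991 | 1,278 |
| 0.01 | e^-0.14 = 0.87 | -0.9998 | about 46,000 |

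The value of 1000 is crossed at a rate a little above 0.05/day.

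**4. Simulation with a linear truth.** There were 500 trials per scenario, with 12 participants and a slope CV of 22% (both from SAP 4.3). Total rises of 11, 50 and 100 h and residual SDs of 10, 20 and 40 h are assumptions; 11 h is a figure in SAP 4.3. With the intercept removed, the condition number for B and k exceeded 1000 in 38% to 99% of trials, and k sat on its numerical lower bound in 37% to 51%. The fitted 0-14 change was still recovered. For an 11 h rise at SD 10 h its mean was 11.15 h, against 11.14 h from a straight line. The largest gap between the two means in the nine scenarios was 0.75 h (11 h rise, SD 40 h).

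**The case against.** The strongest reply is that the SAP does not close its list. SAP 10.3 calls itself a summary, 10.3.1 allows further functions if the data call for them, and 10.3.5, 10.3.6 and 10.3.8 provide visual checks, AIC and objective-function comparison, and a requirement of no important trends. The bracket about CFU may attach to the bi-linear form alone. With the TTP heading, that suggests a straight line was intended and the wrong equation printed. The protocol's wording also ends with a non-linear option.

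Much of this stands. A reader might infer that the SAP forbids a linear TTP model or breaches the protocol. It does neither: it narrows the list in print and leaves the rest to a choice made after the data are seen, in an open-label study. On either reading of the bracket, the equation is missing.

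The diagnostics help when the misfit is large but not always when it is small. The residual sum of squares in step 2 is (1 - 0.8864) x 227.5 = 25.84 h^2 for a 1 h/day rise. Scaled to 11 h over 14 days it is 25.84 x (11/14)^2 = 15.95 h^2 per participant, or 191 h^2 for 12. At SD 10 h this costs roughly 191 / 100 = 1.9 points of objective function, which is easily overlooked. For a 50 h rise the cost is 1.9 x (50/11)^2, about 39 points, which would be seen.

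A reader might also infer that the exponential would have to be rejected. SAP 10.3.8 only prefers a condition number below 1000 and lets a model be justified without it. No covariance-step failure was shown. The calculation is for a single curve without random effects, whereas the SAP plans one model per endpoint across arms, which may help to fix the shape. Finally, model-free observed changes for the same windows are tabulated (Table 14.4.9).

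**Conclusion.** The point holds as a defect in the printed equations. The undefined Day 0 value and the slope that cannot be zero or negative follow from the algebra and need no assumption. The distortions of 3.5, 1.65, 0.50 and 0.35 times the true rate, and the weak separation of asymptote and rate, rest on a near-linear rise. Neither document predicts that shape for RESP301; it is a plausible case that the candidate set should cover.

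A reader might take these ratios to mean that the headline result is biased. The documents and the calculation do not support that: the whole-period average moves by 3% on Days 1-14 (4% on Days 0-14 with a shifted origin), and the exponential recovers it. No claim is made about the standard error of the primary slope. The effect falls on the sub-period and daily tables, the exploratory Day 14-15 comparison, the stability of the exponential's parameters, and the fit between the logarithmic form and the Stage 2 criterion. It should be corrected.

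**What to change.** In SAP 10.3.1:

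- Add TTP = A + alpha x t as a candidate, with alpha free in sign. Exempt this slope from the exponential random-effect form in SAP 10.3.2, which bounds individual parameters at zero.
- Add a bi-linear TTP candidate with node k, as already written for CFU.
- Define the time origin for the logarithmic form, including how the Day -2 and Day -1 samples enter.
- Align the introductory sentence and the TTP heading with Protocol 1.2, so that labels and equations agree.

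Choose among the candidates with the AIC, objective-function and diagnostic criteria already in SAP 10.3.6. No fitting order needs to be prescribed. The best time is before the Stage 1 interim model is fitted, because SAP section 9 sends the interim EBA analysis to the same section. The cost is two equations, some wording and slightly more analysis work, with no new data.
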